APPENDIX B: Patient Questionnaire Table of Contents

Questionnaires are representations of the on-line questionnaires.

Domain (Appendix location)	Assessment Tool	T1	T2	T3
Background Questionnaires (Appendices C, D, E)	Sociodemographic questions Medical History Reproductive History Pre-treatment Fertility Experiences Post-treatment Fertility Experiences	X X X X X		
Decisional Conflict (Appendix F)	Decision Conflict Scale	X	X	X
Unmet Information Needs (Appendix G)	Investigator-designed items about fertility and family-building information needs	X	X	X
Cognitive, Emotional, and Behavioral Functioning (Appendices H, I, J)	Illness Perceptions Questionnaire – Revised Reproductive Concerns after Cancer Scale Impact of Events Scale-Revised	X X X	X X X	X
Self-Efficacy (Appendix K)	PROMIS General Self-Efficacy PROMIS Self-Efficacy for Managing Emotions	X X	X X	X
Internet Use (Appendix L)	e-Health Impact Questionnaire Part 1 Part 2	X	X	
Financial Stress (Appendix M, N)	COmprehensive Score for Financial Toxicity InCharge Financial Distress/Financial Well-being Scale	X X		
Uncertainty Management (Appendix O)	Uncertainty Management Preferences	X		
Health Literacy (Appendix P, Q)	Brief Health Literacy Screener Health Literacy – Young Adult	X X		
Actions & Concomitant Care (Appendix R)	Actions & Care (investigator designed)		X	X
Website Impact (Appendix S, T, U)	Stage of Decision Making Preparation for Decision Making Family-building Website Use	X X X	X X X	
Website Feedback (Appendix V)	Website feedback (investigator designed)		X	

APPENDIX C: Background Questionnaire

1. Date of Birth: ____ / ____ / ____
2. With which of the following groups do you most identify? (Select all that apply)
 - White
 - Black
 - American Indian or Alaskan Native
 - Asian or Pacific Islander
 - Other:

 - Unknown
 - Prefer not to answer
3. Are you Hispanic/Latina?
 - No
 - Yes
 - Prefer not to answer
4. With which of the following religious groups do you most identify?
 - Christian, Catholic
 - Christian, all other denominations
 - Jewish, Orthodox
 - Jewish, Non-Orthodox
 - Muslim
 - Buddhist
 - Hindu
 - Other world religions
 - Other faiths
 - Not affiliated with a formal religion
 - Don't Know/Refused
5. What is the highest level of education you have completed?
 - Some high school, but no degree
 - High school degree
 - Vocational training after high school, other than college
 - Some college, but no degree
 - College degree
 - Post-graduate degree
 - Prefer not to answer
6. Which of the following best describes your current student status?
 - I am a full-time student
 - I am a part-time student
 - I am not enrolled in school
 - Prefer not to answer

7. Which of the following best describes your current employment status?
 I am employed full-time
 I am employed part-time
 I am not employed
 Prefer not to answer
8. Over the past year, what is the total income of the household you live in?
 Less than \$50,000
 \$50,000 - \$100,000
 Greater than \$100,000
 Unknown
 Prefer not to answer
9. What best describes the locality or environment in which you live?
 Urban
 Suburban
 Rural
 Prefer not to answer

APPENDIX D: Medical History

1. Have you ever been treated for a serious medical illness(s) other than cancer (eg, asthma, diabetes, hypertension, etc.)

No

Yes. If yes, please indicate: _____

2. Date of cancer diagnosis: ____ / ____ (MM / YY)

3. Cancer Type:

4. Cancer Stage:

5. Where did you receive most of your cancer treatment?

Pediatric cancer clinic

Adult oncology clinic

Specialized young adult or "teen" cancer clinic

6. Date of last cancer treatment: ____ / ____ (MM / YY)

7. **Please circle** which type(s) of treatment you had:

Surgery

Chemotherapy

Radiation Treatment

Other

If other, what other type of treatment did you receive? _____

8. Are you still on hormonal therapy?

Yes; if yes, how long are you expecting to be on hormone therapy? _____

No

9. Date of last menstrual cycle: ____ / ____ / ____

10. Which of the following best describes your current menstrual periods?

I have regular periods (occurring about every 26 to 35 days) and I am NOT taking birth control pills or female hormones

I have regular periods (occurring about every 26 to 35 days) and I am taking birth control pills or female hormones

My periods are irregular (differing number of days between periods)

I have not had a period for at least 12 months.

I stopped getting my menstrual periods at age _____

I am currently pregnant or my last pregnancy ended within the past 6 months.

APPENDIX E: Reproductive History

1. Do you currently have children?
 Yes; if yes, how many? _____
 No
2. Did you have any children before beginning cancer treatment?
 Yes – conceived naturally; if yes, how many? _____
 Yes – through fertility treatment (for example, IVF) .
 Yes – adopted or fostered
 No
3. Do you want to have children (or more children) at some time in the future?
 Yes
 No. Contact study team or [name]
 Unsure
4. When would you hope to have a child in the future?
 I do not want to have a child (or more children)
 I am not sure if I want to have a child (or more children)
 I am currently trying to get pregnant
 I am currently trying to adopt or find a surrogate
 Probably in the next 2 years
 Probably in the next 2 to 5 years
 Probably more than 5 years from now
5. Do you believe that your cancer treatment affected your fertility (your ability to conceive or have children naturally)?
 I believe it definitely affected my fertility
 I believe it probably affected my fertility
 I do not know
 I believe it probably did NOT affect my fertility
 I believe it definitely did NOT affect my fertility

APPENDIX E Reproductive History

Pre-treatment Fertility Experience

Before you started cancer treatment...

6. Did your oncologist, nurse, or other healthcare professional discuss fertility with you?
 Yes
 No
 I don't remember
7. Do you feel that you were well informed about the option to potentially preserve your fertility by freezing eggs or embryos before treatment?
 I was satisfied with the amount of information
 I was not satisfied – I did not receive enough information
 I was not satisfied – it was not discussed at all
 I was not interested in receiving this information, or it was not applicable to me
8. Did you meet with a fertility specialist or reproductive endocrinologist before starting treatment?
 Yes, I met with a fertility specialist or reproductive endocrinologist (but have not pursued fertility preservation)
 No, I did NOT meet with a fertility specialist or reproductive endocrinologist even, even though I was referred to one
 No, I did NOT meet with a fertility specialist or reproductive endocrinologist because I did not know about this or was not referred
 No, I did NOT meet with a fertility specialist or reproductive endocrinologist because I was not interested in fertility preservation
 I don't remember

Did you undergo fertility preservation before starting your cancer treatment?

Yes
 No
 Prefer not to answer

If Yes, what did you do? Check all that apply

Egg freezing
 Embryo freezing
 Ovarian tissue freezing
 Ovarian transposition
 Ovarian suppression
 Other type of fertility preservation: _____

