For **Study Objective 2**, for each outcome variable, we will examine the distributional qualities, extent of missing data, and satisfaction of assumptions of randomness (ie, MAR, MCAR). Descriptive statistics will evaluate sample characteristics. Covariates with significant relationships with the decisional conflict scale (DCS) will be included in final models. To obtain an effect size estimate of the decision aid in reducing decisional conflict, pairwise t-test will evaluate change in DCS mean scores from T1 to T2. A two-sided hypothesis test of the within-subject difference in adjusted means will test the null hypothesis ($H_0: \mu_1 = \mu_2$) at $\alpha = 0.05$. Rejection of the null hypothesis will indicate a significant within-subject DCS mean change from T1 to T2 ($H_1: \mu_1 > \mu_2$). Effect size estimates (Cohen’s d) will be calculated and reported. On an exploratory level, we will examine T1 to T3 and T2 to T3 mean differences to characterize the DCS trajectory. Similar procedures will analyze changes in the IPQ-R, RCACS, PROMIS Self-Efficacy, and the IES-R as secondary outcomes, controlling for key covariates. The Stage of Decision Making Scale will be assessed, and descriptive statistics will evaluate whether use of the decision aid website impacts readiness to engage in decision making, progress in making a choice, and receptivity to considering or re-considering options between timepoints T1 and T2 and between timepoints T2 and T3. The Preparation for Decision Making Scale will be assessed, and descriptive statistics will evaluate whether use of the decision aid website impacts perception of how useful a decision aid or other decision support intervention is in preparing the respondent to communicate with their practitioner at a consultation focused on making a health decision. The eHealth Impact Questionnaire-Part 2 will be assessed and descriptive statistics will evaluate the impact of using the decision aid website across three domains: 1) confidence and identification of health concerns, 2) information and presentation of website material, and 3) understanding and motivation to manage health issues.

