APPENDIX E, Reproductive History
Post-treatment Follow-up Care

After you finished your cancer treatment...

9. Has your oncologist or other health care professional discussed fertility with you during your follow-up care?

Yes, I was satisfied with the amount of information I received
 Yes, but I was NOT satisfied with the amount of information I received
 No, it was not discussed at all
 No, I was not interested in receiving this information, or it was not applicable to me
 I don't remember

10. Has your oncologist or other health care professional discussed risk for infertility or premature menopause with you during your follow-up care?

Yes, I was satisfied with the amount of information I received
 Yes, but I was NOT satisfied with the amount of information I received
 No, it was not discussed at all
 No, I was not interested in receiving this information, or it was not applicable to me
 I don't remember

11. Has your oncologist or other health care professional discussed fertility preservation or alternative family-building options (such as adoption) with you during your follow-up care?

Yes, I was satisfied with the amount of information I received
 Yes, but I was NOT satisfied with the amount of information I received
 No, it was not discussed at all, but I wish it had been
 No, I was not interested in receiving this information, or it was not applicable to me
 I don't remember

12. Have you been referred to a fertility specialist or reproductive endocrinologist since your treatment ended?

Yes, I was referred and I have met with a fertility specialist or reproductive endocrinologist (but have not pursued fertility preservation)
 Yes, I was referred but I have NOT met with a fertility specialist or reproductive endocrinologist
 No, I was not referred, but I am interested in this
 No, I was not referred, but I pursued it on my own
 No, I was not referred and I am NOT interested in this
 I don't remember or am unsure.

13. Have you met with a fertility specialist or reproductive endocrinologist since your treatment ended?

Yes

No

A fertility evaluation is generally done by a reproductive endocrinologist, a gynecologist who specializes in fertility. Blood is drawn to measure fertility hormone levels and an ultrasound is done so the doctor can see your ovaries.

14. Have you undergone a fertility evaluation with a reproductive specialist since your cancer treatment ended?

Yes → go to Question 35

No → go to Question 34

Unsure → go to Question 34

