Prefer not to answer → go to Question 34

15. Have you considered having a fertility evaluation and/or undergoing fertility preservation in the future?

Yes – I have decided to do this / have done this already

Yes – I am thinking about doing this

No – I have not thought about doing this

Prefer not to answer

16. Have you undergone fertility preservation since completing your cancer treatment?

Yes

No

Prefer not to answer

If Yes, what did you do? Check all that apply

Egg freezing

Embryo freezing

Other type of fertility preservation: _____

17. Have you been told that you will not be able to get pregnant or carry a pregnancy because of your cancer treatment?

Yes

No

I don't remember / I'm not sure

Prefer not to answer

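### Appendix E, Questions 8 and 12: women who met a fertility specialist and did preserve fertility have no accurate answer option

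*Combined protocol and SAP*

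**What the plan says.** Appendix E is part of the background block that Appendix B schedules at T1 only. The relevant items are:

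- **Question 8** asks about a specialist visit before treatment. Its single affirmative option is "Yes, I met with a fertility specialist or reproductive endocrinologist (but have not pursued fertility preservation", where the parenthesis closes. The remaining options are three forms of No and one for not remembering.
- **The next item, unnumbered,** asks "Did you undergo fertility preservation before starting your cancer treatment", with Yes, No or a decline option, followed by a checklist of methods. No skip from Question 8 is printed.
- **Question 12** asks about referral after treatment. Its only referred-and-met option is "Yes, I was referred and I have met with a fertility specialist or reproductive endocrinologist (but have not pursued fertility preservation", again closing the parenthesis there.
- **Question 13** asks "Have you met with a fertility specialist or reproductive endocrinologist since your treatment ended", as a plain Yes or No.
- **Question 14** (fertility evaluation since treatment) carries the skips "Yes → go to Question 35" and "No → go to Question 34". The unsure and decline answers also go to 34. Appendix E ends at Question 17.
- **Question 16** asks "Have you undergone fertility preservation since completing your cancer treatment", followed by methods.

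On use of baseline data, section 5.2 states: "Covariates with significant relationships with the decisional conflict scale (DCS) will be included in final models". It also plans comparisons of completers with non-completers without naming the variables. Appendix B describes the printed forms as representations of the online ones, and section 6.1 says the surveys run in REDCap.

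**The concern.** Questions 8 and 12 each join two facts in one answer: that the woman met a specialist, and that she did not go on to preserve fertility. Women for whom the first is true and the second false have no option that fits. They must tick a Yes that misstates their history, tick a No or a do-not-remember that is false, or leave the item blank.

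The error is systematic, because it falls only on women who preserved fertility. A forced No on Question 8 would put them in the same category as women who never had access to a specialist. This subgroup is informative here: the Appendix F instruction frames the primary scale around a decision on future fertility preservation, so earlier consultation and preservation plausibly relate to the score.

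At stake are two baseline descriptors, the pre-treatment visit rate and the post-treatment referral rate, and any group comparison or covariate model that uses them. The form is given once, so no later visit corrects the answer.

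The skip labels in Question 14 are a separate numbering fault on the same form. They name questions that no appendix prints.

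**Working it through.** No figure in the plan is to be reproduced here. The check compares the response options, counts the items and bounds the error.

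**1. Which facts have an accurate option for a woman who met a specialist and preserved fertility?**

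| Fact | Item | Accurate option? |
|---|---|---|
| Visit before treatment | Question 8 | No |
| Preservation before treatment, and method | Unnumbered item after Question 8 | Yes |
| Referral after treatment (referred, met, preserved) | Question 12 | No |
| Visit after treatment | Question 13 | Yes |
| Preservation after treatment, and method | Question 16 | Yes |

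Question 12 does have an option for women who were not referred but pursued it themselves, so its gap is limited to those who were referred, met a specialist and preserved fertility.

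**2. Where do skip targets 34 and 35 lead?** Appendix C has 9 numbered items, Appendix D has 10 and Appendix E has 17. Numbered continuously, Appendix E would run from 9 + 10 + 1 = 20 to 9 + 10 + 17 = 36. Then:

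- 34 − 19 = 15, so target 34 is Appendix E Question 15.
- 35 − 19 = 16, so target 35 is Appendix E Question 16.

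This routing makes sense: women who have had an evaluation pass over the question about considering one, and everyone reaches Questions 16 and 17. If the unnumbered item were counted as well, 34 − 20 = 14 would send Question 14 back to itself, so that count can be ruled out. The mapping is an inference from item counts; the documents do not state it.

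**3. How far could the pre-treatment visit rate be off?** Take 100 women (the target in section 5.3). Let s be the number who met a specialist before treatment and preserved fertility, and x the number who met one and did not.

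- True rate: (x + s)/100.
- All s record a No: x/100, which is s percentage points too low.
- All s leave it blank: x/(100 − s). The shortfall is s(100 − s − x)/[100(100 − s)], between 0 (when x = 100 − s) and s percentage points (when x = 0).
- All s tick the Yes anyway: the visit rate is right, but the answer contradicts the next item.

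The documents give no value for s. Assuming 10, 20 or 30, the visit rate is understated by between 0 and 10, 20 or 30 percentage points, depending on how those women respond. The same reasoning applies to Question 12, with s the number referred, met and preserved after treatment.

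**The case against.** The strongest reply is that little is lost. Preservation before treatment, preservation after treatment and the post-treatment visit each have an answerable item. The item after Question 8 also identifies the women concerned, so much of the Question 8 error can be repaired without new data. These are background items, not outcomes. The plan names medical characteristics as covariates but not specialist visits or referral. All of this stands, and it limits the point to two facts and a minor rating. It does not defend the parenthetical: preservation is asked separately, so the qualifier adds nothing.

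Three stronger readings are tempting and not supported:

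- **That fertility history in general is wrong or missing.** The other items capture most of it. Only the pre-treatment visit and the post-treatment referral are affected.
- **That the skips lose data or point to omitted questions.** The targets look like labels left over from continuous numbering. The printed forms only represent the online ones, and the live branching is not shown, so loss is possible but not demonstrated.
- **That the trial loses power.** The sample size in section 5.3 rests on a paired t-test of the Decisional Conflict Scale, which uses no Appendix E item. A loss would need Question 8 or 12 to be selected into a model, affected women to leave it blank, no recoding, and deletion of incomplete cases. The plan commits to none of these, and the power of a paired test would not be the power of such a model.

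**Conclusion.** The defect is real and can be read directly from the form. Question 8 and the referred-and-met option of Question 12 cannot be answered truthfully by women who met a specialist and preserved fertility. For that subgroup the pre-treatment visit rate and the post-treatment referral rate will be misclassified or missing, both in the baseline description and in any comparison or covariate model that uses them.

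The size depends on two unknowns: how many participants belong to the subgroup, and which option they choose. The range in the working is illustrative and rests on assumed shares. Section 5.2 also refers to adjusted means and final models, so these items could enter an adjusted analysis if selected; nothing says that they will. The unadjusted T1 to T2 comparison of the primary outcome and its stated power are unaffected. Severity is minor.

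**What to change.** 1. Delete the parenthetical from the affirmative option of Question 8 and from the referred-and-met option of Question 12. No information is lost, because preservation is asked separately for each period.
2. Correct the Question 14 skip labels from 35 to 16 and from 34 to 15, and number the preservation item that follows Question 8 without disturbing those targets.
3. Check the REDCap branching and confirm that every woman reaches Questions 16 and 17. Question 16 is the only direct item on preservation after treatment.
4. For women already enrolled, use the preservation item after Question 8 to flag affected answers, and recode Question 8 to Yes where egg or embryo freezing is ticked. This assumes that those procedures imply a specialist visit. Flag the other methods without recoding them. For Question 12, a Yes to both Questions 13 and 16 identifies women who may be affected but does not show whether they were referred, so report that referral is uncertain for them.

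The cost is a wording and branching edit to one online form, an IRB modification and a short documented recoding rule. The design, sample size and primary analysis do not change.

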APPENDIX E, Reproductive History
Post-treatment Follow-up Care

After you finished your cancer treatment...

9. Has your oncologist or other health care professional discussed fertility with you during your follow-up care?

Yes, I was satisfied with the amount of information I received
 Yes, but I was NOT satisfied with the amount of information I received
 No, it was not discussed at all
 No, I was not interested in receiving this information, or it was not applicable to me
 I don't remember

10. Has your oncologist or other health care professional discussed risk for infertility or premature menopause with you during your follow-up care?

Yes, I was satisfied with the amount of information I received
 Yes, but I was NOT satisfied with the amount of information I received
 No, it was not discussed at all
 No, I was not interested in receiving this information, or it was not applicable to me
 I don't remember

11. Has your oncologist or other health care professional discussed fertility preservation or alternative family-building options (such as adoption) with you during your follow-up care?

Yes, I was satisfied with the amount of information I received
 Yes, but I was NOT satisfied with the amount of information I received
 No, it was not discussed at all, but I wish it had been
 No, I was not interested in receiving this information, or it was not applicable to me
 I don't remember

12. Have you been referred to a fertility specialist or reproductive endocrinologist since your treatment ended?

Yes, I was referred and I have met with a fertility specialist or reproductive endocrinologist (but have not pursued fertility preservation)
 Yes, I was referred but I have NOT met with a fertility specialist or reproductive endocrinologist
 No, I was not referred, but I am interested in this
 No, I was not referred, but I pursued it on my own
 No, I was not referred and I am NOT interested in this
 I don't remember or am unsure.

13. Have you met with a fertility specialist or reproductive endocrinologist since your treatment ended?

Yes

No

A fertility evaluation is generally done by a reproductive endocrinologist, a gynecologist who specializes in fertility. Blood is drawn to measure fertility hormone levels and an ultrasound is done so the doctor can see your ovaries.

14. Have you undergone a fertility evaluation with a reproductive specialist since your cancer treatment ended?

Yes → go to Question 35

No → go to Question 34

Unsure → go to Question 34

Prefer not to answer → go to Question 34

15. Have you considered having a fertility evaluation and/or undergoing fertility preservation in the future?

Yes – I have decided to do this / have done this already

Yes – I am thinking about doing this

No – I have not thought about doing this

Prefer not to answer

16. Have you undergone fertility preservation since completing your cancer treatment?

Yes

No

Prefer not to answer

If Yes, what did you do? Check all that apply

Egg freezing

Embryo freezing

Other type of fertility preservation: _____

17. Have you been told that you will not be able to get pregnant or carry a pregnancy because of your cancer treatment?

Yes

No

I don't remember / I'm not sure

Prefer not to answer

